[figure not shown]
Safety and clinical outcomes assessments will be collected bi-weekly for a total of four data collection timepoints.

A study design schematic is provided in Figure 1 below.

¹ Hofmann, S. G., Asnaani, A., Vonk, I. J., Sawyer, A. T., & Fang, A. (2012). The efficacy of cognitive behavioral therapy: A review of meta-analyses. Cognitive therapy and research, 36(5), 427-440

² Dobson, D., & Dobson, K. S. (2018). Evidence-based practice of cognitive-behavioral therapy. Guilford Publications.

³ Beukes EW, Manchaiah V, Allen PM, Baguley DM, Andersson G. Internet-Based Interventions for Adults With Hearing Loss, Tinnitus, and Vestibular Disorders: A Systematic Review and Meta-Analysis. Trends Hear. 2019 Jan-Dec;23:2331216519851749.

All study activities are decentralized and will not require participants to visit a site in person. A centralized Principal Investigator and clinical study staff will conduct study activities remotely. Participants will complete all study activities remotely.

Measures

Primary outcomes are a change from baseline in Tinnitus Functional Index (TFI) and TFI responder rate at 6 weeks. A reduction of 13 points is considered clinically significant for the TFI.⁴

Eligibility

Participants must satisfy the following criteria before entering the study:

- 1. Participant scores \geq 25 on the Tinnitus Functional Index.
- 2. Participant has experienced symptoms of tinnitus for at least 3 months.
- 3. Participant is at least 18 years of age at the time of consent.
- 4. Participant resides in the United States.
- 5. Participant is able to speak, read, and understand English.
- 6. Participant has access to an iOS or Android smartphone with the ability to complete study tasks.
- 7. Participant is able to commit the time required to complete therapy modules and study assessments.

Participants who meet any of the following criteria will be excluded from participating in the study:

- 1. Participant scores ≥ 2 on item 9 (suicidal thoughts) of the Beck's Depression Index (BDI).
- 2. Participant has been hospitalized for psychiatric reasons within 12 months of screening.
- 3. Participant is currently enrolled in or plans to enroll in another clinical study that could impact outcomes of this trial.
- 4. Other exclusions may apply if determined by the clinical study team that participation may be impacted.

Sample Size

This study will enroll 125-250 total participants.

⁴ Meikle MB, et al. *Ear Hear*. 2012;33(2):153-76

Intervention

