MHNA-003 is an investigational software as a medical device (SaMD) built for mobile usage.

MHNA-003 comprises five total sessions. Each session includes several lessons which provide components of cognitive behavioral therapy.

We recommend that participants complete one lesson of MHNA-003 per day. One lesson takes approximately 10-15 minutes. At the recommended pace the study sessions will take participants approximately 30 days to complete all lessons. This study protocol includes twelve additional days (42 total study days) to accommodate unanticipated interruptions to therapy progress.

MHNA-003 is available via a downloadable application for iOS and Android smartphones. Access to MHNA-003 and technical assistance will be provided to participants at no charge.

MHNA-003 is considered a non-significant risk (NSR) device. The risks associated with using MHNA-003 are akin to those associated with using a mobile app for 10-15 minutes per day.

Statistical Analysis

Analyses of feasibility and participant-reported clinical outcomes primarily rely on descriptive statistics. Inferential statistics are used to explore potential preliminary associations. All statistical analyses are performed using Stata 18.0 and focus on the intent-to-treat population.

Baseline demographics and participant characteristics are summarized using descriptive statistics. Specifically, means, standard deviations (SD), and ranges are assessed for continuous variables and assessment scores typically treated as continuous. Data are presented as mean ± SD. For categorical data, n's and percentages are calculated.

Statistical analysis techniques are employed to evaluate changes in patient-reported outcomes over time. Magnitude and statistical significance for change from baseline are tested using single factor mixed effects linear GLS regression modeling. This type of model is able to handle missing data due to attrition and can also be utilized for complete datasets. The need for random effects is tested in all cases using the Hausman comparison⁵ and Breusch and Pagan Lagrangian multiplier test.⁶ The Breusch-Pagan and Cook-Weisberg test for heteroscedasticity⁷ is also utilized. Mean, standard error of the mean, and 95% confidence intervals are calculated for changes from baseline. Wald chi-square tests assess the significance of changes from baseline over time.

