Six-week responder rates are evaluated utilizing multiple imputation modeling to account for missing data. Responder rates are imputed in the ITT population utilizing logistic models. Four baseline factors are included in the imputation model: age, sex, baseline GAD-7 score, and baseline PHQ-8 score. It is possible that these help to describe relevant populations for level of outcome. In addition, program adherence is included as a covariate because outcome level is

⁵ Hausman JA. *Econometrica*. 1978;46:1251-1271.

⁶ Breusch TS & Pagan AR. *Econometrica*. 1979;47(5):1287-1294.

⁷ Cook RD & Weisberg S. Biometrika. 1983;70(1):1-10.

hypothesized to be related to program adherence. Sensitivity analysis is performed by removing the auxiliary variables from the imputation regression. Standard error of the mean and 95% CI are calculated for the responder rates.

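### The only missing-data sensitivity analysis for the 6-week responder rate cannot show what happens if participants missing at week 6 respond less often than similar observed ones; adding that check costs little.

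*Combined protocol and SAP*

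**What the plan says.** The Measures section of the combined protocol and SAP states: "Primary outcomes are a change from baseline in Tinnitus Functional Index (TFI) and TFI responder rate at 6 weeks".

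The Statistical Analysis section covers missing data for the responder rate:

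- Method: "Six-week responder rates are evaluated utilizing multiple imputation modeling to account for missing data".
- Model: "Responder rates are imputed in the ITT population utilizing logistic models".
- Baseline predictors: "Four baseline factors are included in the imputation model: age, sex, baseline GAD-7 score, and baseline PHQ-8 score".
- Post-baseline predictor: "program adherence is included as a covariate because outcome level is" expected to depend on it.
- Sensitivity analysis: "Sensitivity analysis is performed by removing the auxiliary variables from the imputation regression".
- Precision: "Standard error of the mean and 95% CI are calculated for the responder rates".

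The documents contain no delta-adjusted, tipping-point, worst-case or missing-as-non-response analysis. They do not say which predictors count as auxiliary, and they give no expected response rate or attrition. The plan does not claim that its sensitivity analysis demonstrates robustness.

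**The concern.** Both the main and the reduced imputation fit a logistic model to participants with an observed week-6 response and use it, without any shift, for those whose response is missing. Each therefore assumes that, given the predictors kept, missing participants respond like observed ones. Removing predictors changes what is conditioned on but leaves that assumption in place. This is so whether the auxiliary variables are adherence alone, the baseline factors or all five.

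The departure is plausible. Follow-up is entirely remote and self-reported, and someone who uses the app without improving may simply not answer at week 6. Judged by the named predictors, that person looks like someone who improved. If non-responders are missing more often than those predictors explain, the reported rate is too high, and neither the planned check nor the 95% CI reveals it.

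**Working it through.** The plan states no figure to reproduce. The enrolment range of 125 to 250 comes from the Sample Size section. Every response rate, missing share and effect size below is assumed.

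**1. Closed form.** Let p be the response rate among those observed, d the share missing, and k the factor on the response odds of the missing.

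- Odds among the observed: o = p/(1−p)
- Rate among the missing: q = k·o/(1+k·o)
- Overall rate = (1−d)·p + d·q

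For p = 0.5, o = 1. With k = 0.5, q = 0.5/1.5 = 0.333. At d = 0.3 the overall rate is 0.7×0.5 + 0.3×0.333 = 0.450, a drop of 5.0 points.

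Overall rate (%) at p = 0.5:

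| Missing | k=1 | k=0.75 | k=0.5 | k=0.25 | k=0 (non-response) |
|---|---|---|---|---|---|
| 10% | 50.0 | 49.3 | 48.3 | 47.0 | 45.0 |
| 20% | 50.0 | 48.6 | 46.7 | 44.0 | 40.0 |
| 30% | 50.0 | 47.9 | 45.0 | 41.0 | 35.0 |
| 40% | 50.0 | 47.1 | 43.3 | 38.0 | 30.0 |

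For p from 0.4 to 0.6 and d from 0.1 to 0.4, halving the odds lowers the rate by 1.5 points (p = 0.4, d = 0.1) to 6.9 points (p = 0.6, d = 0.4).

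**2. Comparison with the CI.** An approximate half-width from observed cases is 1.96·√(0.25/((1−d)·n)). At d = 0.3 this is 1.96·√(0.25/87.5) = 10.5 points for n = 125 and 1.96·√(0.25/175) = 7.4 points for n = 250. At d = 0.1 it is 9.2 and 6.5 points. The 5.0-point shift is smaller than either half-width at 30% missing, but it is a bias, which the interval does not account for.

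**3. Can the planned check reveal the bias?** Large-sample simulation with 2,000,000 participants: logit P(response) = 0.7·A − 0.3·B, where A is standardized adherence and B a standardized composite of the four baseline factors. The true rate is 49.97%. Missing responses take the predicted probability, which is the large-sample limit of logistic imputation. Where missingness depends on adherence, its slope on A is −0.7.

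Estimated rate (%):

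| Missingness | Missing | Main | Adherence removed | Baseline removed | All removed | Main, odds ×0.5 |
|---|---|---|---|---|---|---|
| Adherence only | 30% | 49.97 | 52.94 | 49.97 | 52.94 | 45.71 |
| Adherence, plus doubled missingness odds in non-responders | 30% | 54.48 | 57.42 | 54.58 | 57.50 | 49.96 |
| Doubled odds only | 30% | 54.50 | 55.00 | 54.59 | 55.09 | 49.96 |
| Adherence only | 10% | 49.97 | 50.99 | 49.97 | 50.99 | 48.58 |
| Adherence, plus doubled odds | 10% | 51.35 | 52.46 | 51.38 | 52.49 | 49.96 |
| Doubled odds only | 10% | 51.45 | 51.61 | 51.48 | 51.65 | 49.96 |

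At 30% missing, removing adherence or all predictors moves the rate by about 3 points in the first row, where the main bias is 0, and in the second, where it is 4.5 points. In the third row the bias is again 4.5 points but the gap is at most 0.6. Neither agreement nor disagreement between the two results is informative about this bias. With low adherers missing more and responding less, the reduced model moves the rate up, away from the pessimistic direction.

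**4. Other effect sizes and trial-sized samples.** At 30% missing, the effect of A on response (0.3, 0.7, 1.1) was crossed with its slope on missingness (−0.3, −0.7, −1.1). The gap was 0.6 to 6.0 points with no bias, and also 0.6 to 6.0 points with a bias of 3.9 to 4.9. Over 4,000 replicates of the first two scenarios, the 5th to 95th percentiles of the gap (all predictors removed) were 0.9 to 5.6 (unbiased) and 0.8 to 5.7 (biased) at n = 125, and 1.5 to 4.7 and 1.5 to 4.8 at n = 250.

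**5. What the delta factors do.** The 0.5 factor recovers the true rate under doubled odds by construction. Under adherence-only missingness it gives 45.71%, which is 4.3 points too low. The factors give a range, not a correction.

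**The case against.** The strongest reply is that no stated conclusion changes. The Objectives section presents the trial as a single-arm pilot whose results are hypothesis-generating, and the analysis plan says: "Analyses of feasibility and participant-reported clinical outcomes primarily rely on descriptive statistics". There is no responder threshold, and the illustrative shifts sit inside the CI. This stands, and it limits the point to a recommended addition.

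All sizes are assumed. That also stands: the simulations establish the logic, not how large the problem is in this trial.

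Adherence is already in the main model and absorbs the part of lower response that it explains. True; the concern is the remainder.

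The trial collects outcomes every two weeks, yet no TFI score is among the named imputation predictors. If missingness depended only on adherence and an observed interim score, adding that score would remove the bias. A check on assumed values at 30% missing had the planned model about 4.7 to 5.1 points too high and the bias gone once the score was added. That is a useful complement, but it does not help with participants who leave before giving an interim score, or with missingness driven by the unseen week-6 result.

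Factors of 1 or less only lower the rate, whereas improvers might also skip week 6. With odds ×2, p = 0.5 and 30% missing, q = 2/3 and the rate is 0.35 + 0.20 = 55.0%. A factor above 1 is a fair optional addition.

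Finally, missing week-6 data is not the same as stopping the app, and counting missing as non-response bounds only the proportion in the enrolled sample, before sampling error. Both are correct and should be reflected in the labels.

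**Conclusion.** The concern holds. The planned sensitivity analysis shows dependence on the removed predictors, notably adherence, and is worth keeping for that. Under any reading of auxiliary variables it cannot examine missing participants responding less often than similar observed ones, and no other planned analysis does.

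If half of those observed respond, halving the response odds of the missing costs 1.7 to 6.7 points as missingness goes from 10% to 40%. These sizes rest on assumed response rates, missing shares and odds factors; the conclusion about what the check can detect does not. This is a cheap improvement to a primary outcome's reporting, not an error that invalidates the pilot.

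**What to change.** Keep the planned imputation and its sensitivity analysis, and add:

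- **(a)** The responder rate among all enrolled with missing week-6 response counted as non-response, labelled a lower bound for the proportion in the enrolled sample.
- **(b)** Delta-adjusted versions of the same logistic imputation, multiplying the imputed response odds of participants with missing week-6 response by prespecified factors, for example 0.75, 0.5 and 0.25. This is done by adding the log of the factor to the linear predictor. Give each version its 95% CI.

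Report (b) as a range and not as a corrected estimate, next to the observed percentage missing at week 6.

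The cost is a few lines of analysis on the existing imputation model, with no new data, participants or assessments. The downside is slightly more reporting and a less favourable bound: if 50% of those observed respond, (a) gives 45.0% at 10% missing and 35.0% at 30% missing.
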